- Rather, a *randomized encouragement design* is adopted in which respondents in randomly selected barangays will be offered the opportunity to enter a lottery for a money prize on condition of attending a RHU/CHC for a checkup within a month. The lottery will have a selection probability of 10% and a prize of 5,000 PHP. There will be one lottery within each of the selected barangays.

- The offer of a lottery ticket will be used to instrument presentation for checkup at RHU/CHC allowing the effect of the latter on predicted 10-year CVD risk, plus risk factors (smoking, BMI, blood pressure), hypertension diagnosis and medication at follow-up to be identified.
- Specifically, we will estimate the regression model,

$$Y_{it} = \gamma Y_{it-1} + \beta x_{it-1} + \tau \,\hat{s_i} + \mu_{it} \tag{6.1}$$

where Y_{it} represents the outcome variable (e.g. predicted CVD risk) at follow-up and \hat{s}_i is the predicted value of a binary variable that equals one for those who attended a RHU/CHC for a checkup, and zero otherwise. The prediction is obtained from the first stage regression described in [H6b] that makes use of the random offer of entry to the lottery. Y_{it-1} and x_{it-1} are the outcome and covariates respectively at baseline. Note that only individuals that are either in the lottery incentive group or in the control group are used for this regression.

• The instrumental variable estimate of τ is an estimate of the impact of a RHU/CHC checkup on the outcome for those induced to present for checkup by the lottery offer who would not have presented for a checkup otherwise.

[H6b] The lottery offer is a strong instrument for presentation at a RHU/CHC for a checkup.

Test:

• Using both the treated respondents who are offered the lottery prize and the control respondents who are not, we will regress a binary variable indicating RHU/CHC attendance (s_i) on a binary variable indicating whether or not the lottery prize was offered (L_i) , i.e.

$$s_i = \gamma Y_{it-1} + \beta x_{it-1} + \kappa L_i + u_i.$$
(6.2)

 $\hat{\kappa} > 0$ indicates that the lottery offer raises attendance. We will test for weakness of the instrument.

[H6c] Individuals who have a preference for risk respond more to the offer of a lottery prize. Thus, the intervention has a larger effect on individuals who potentially engage most in lifestyles that bring exposure to CVD risk.

Elaboration

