- The likelihood insensitivity parameter, α_i , and the utility curvature parameter, r_i , will be identified for each individual *i* using their responses to hypothetical lottery (in gain domain) choice questions specifically designed for use in a survey context and previously used in the Philippines to estimate risk preferences (Van Wilgenburg et al., 2017).
- First, we will test whether compliance varies with a composite measure of risk aversion that comprises both utility curvature and likelihood insensitivity. Using r_i and α_i we will compute

each individual's certainty equivalent of the lottery (CE_i) , and subtract this from the expected value of the lottery (EV = 500) to get the risk premium R_i . This is calculated for all individuals irrespective of whether they are in the treatment group offered the lottery. $R_i > 0$ indicates risk aversion, $R_i < 0$ indicates risk loving and $R_i = 0$ is risk neutrality.

• We will estimate the following regression model,

$$s_i = \gamma Y_{it-1} + \beta x_{it-1} + \psi_1 L_i + \psi_2 R_i + \psi_3 L_i \times R_i + u_i.$$
(6.3)

- ψ_1 corresponds to the lottery response of risk neutral individuals.⁴ This will be positive if the expected gain from the lottery (500 PHP) is sufficient to bridge the shortfall of the expected health gain of the checkup from its cost. In the absence of the lottery incentive, this shortfall presumably explains why the individual does not go for a checkup. If the estimate of this parameter is not significantly greater than zero, we will learn that the perceived gains of a checkup fall short of the costs by more than 500 PHP.
- $\psi_3 < 0$ corresponds to greater compliance among more risk loving individuals.
- Because the estimates of the individual specific risk parameters, and so the risk premium, can be expected to be noisy, we will also try an alternative specification that enters binary indicators of whether the respondent is risk loving or risk averse (interacted with the lottery indicator) into the first stage regression, with risk neutral being the reference category.
- After having established whether compliance varies with a composite measure of risk attitudes, we will explore whether response to the incentive varies with utility curvature and likelihood insensitivity separately. We will estimate the following type of regression model,

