5.3 Lottery incentive for CVD risk assessment

The goal of the second intervention is to evaluate the effectiveness of the PhilPEN program in delivering primary prevention of CVD. This will be achieved by offering randomly selected respondents a ticket for a lottery with a money prize on condition that they visit a RHU/CHC for a checkup. There will be one prize per barangay giving each respondent a one in ten chances of winning P5000 (US\$100). The prize is equivalent to approximately 14 days earnings at the regional minimum wage⁵. This *randomized encouragement design* will induce exogenous variation in patients accessing the PhilPEN program allowing its impact to be estimated.

As noted in Section 3.1, there are potential weaknesses in implementation of the PhilPEN program and the purpose of this component of the experiment is to establish the effectiveness of the program as it is currently implemented. For that reason, there is no supply-side component to the intervention. Respondents will simply be told that they can enter a lottery if they go to the RHU/CHC for a checkup. The health facilities will be told to conduct an assessment deemed appropriate for any particular patient that requests to be issued with a lottery ticket. No instructions will be given that the facilities should follow the PhilPEN protocol. We will evaluate whether they do implement the protocol for patients who qualify (by age if nothing else) for full risk screening.

The remainder of this sub-section describes the logistics of the lottery intervention.

Designating a RHU/CHC point person. The agreement will state that the MHO/CHO should designate a point person in the RHU/CHC facility who will be responsible for handing out the lottery tickets. This should be one of the medical staff (e.g. the rural health nurse, midwife or the MHO/CHO, or PhilPEN coordinator) who performs or delegates the performance of the PhilPEN profiling and screening. The identity of this point person will be included in the information provided by enumerators to the lottery recipients.

Voucher and ticket. A voucher will be given by the enumerator to those deemed eligible for the lottery intervention at the end of the interview. This voucher will be surrendered at the facility to the RHU/CHC point person in exchange for a lottery ticket. The voucher and ticket will both be pre-numbered with the same number.

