- b. *After the interview.* If the respondent is deemed eligible for the lottery intervention, the enumerator will read from a prepared script informing that the respondent is eligible to enter the lottery and that they can claim the ticket from a designated point person at the health center. The script will make it clear that the voucher only entitles them to a lottery ticket and that their name will not be entered if they do not claim the ticket by attending the RHU/CHC for a checkup. The script will also make it clear that they can only claim the ticket after a certain date (possibly two days from receipt of the voucher) and only until a specific date (one month after the interview). The script will also inform the respondent the prize money for the lottery and the chance of winning. The enumerators will be given a prepared answer to give if they are asked whether everyone can enter the lottery. The enumerator will ask the respondent to sign a form indicating that they have understood the terms of the voucher and the lottery.
- c. *Tagging the recipients*. The respondents who receive the vouchers will be tagged by the survey firm. The questionnaire will include fields that indicate whether the respondent is eligible, whether the respondent received the voucher, the date of the receipt of the voucher, and the voucher number.

Instructions to the RHU/CHC point person. To verify the identity of the person claiming the lottery ticket, the point person will be instructed to ask for the name, address, birthday and age as of last birthday, and mobile number of the respondent or any family member. These details will be recorded on a form to be submitted to UPecon. The point persons will not be explicitly instructed to follow the PhilPEN protocol. Rather, they will be told to assess the patients claiming the lottery ticket as they would any other person attending the RHU/CHC for an assessment. Given the sample only contains individuals aged 40+, recording of the person's age should alert the RHU/CHC that, consistent with the PhilPEN protocol, screening should be conducted.

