The information will be recorded on the detachable portion of the lottery ticket (similar to the usual raffle tickets) so that it looks authentic. The point person will then collect the voucher, release the lottery ticket with the same number as that on the voucher and have the recipient sign a receipt. We will leave it to the point person to convince the lottery voucher recipient to undergo any assessment deemed appropriate and to release the ticket afterwards.

UPecon recording of who went to the clinic. Part of the tasks of the RHU/CHC point person is to collate information on who among the voucher recipients have gone to the clinic to claim their tickets. We will request the point person to text a designated number (UPecon hotline) with the name, age, voucher and ticket number that have been claimed, and the contact details of the recipient, immediately after the lottery ticket has been claimed (at the end of each day). After the designated time period allowed to claim tickets, the UPecon R4D team will collect the ticket stubs and vouchers from the RHU/CHC point person.

Lottery draw. The UPecon Team will be responsible for drawing the lottery winners. During the ticket claiming period, the UPecon team will update the list of respondents who have claimed their tickets based on the SMS and email messages of the RHU/CHC point persons. The UPecon team will validate this with the list of voucher recipients submitted by the survey team. Matching voucher and ticket numbers will be included in the list of lottery entries. Once the claim period for the tickets has passed, one week will be allowed for all the claimed ticket numbers to be transmitted to the UPecon team and for all ticket stubs and vouchers to be collected from the RHU/CHCs by the UPecon team. One winner will be drawn from each barangay included in the lottery intervention. If there are no claimants of the lottery tickets from the particular barangay, no winner will be drawn. Once the winners are drawn, an SMS message will be sent to the respondent informing them that they have won and for them to expect a message as to how the prize can be claimed. They will also be informed to designate a representative should they not be available to receive the prize.

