Table 3 Estimates of intra cluster correlation coefficients for CVD risk factors at the level of primary care practices in North America

	Eastern Ontario	Rhode Island and Massachusetts	Vermont				
	Singh et al (2015)	Parker et al (2005)	Littenberg & MacLean $(2006)^{\pm}$				
Systolic Blood Pressure	0.054	0.047	0.042				
Low Density Lipoprotein	0.035	0.006	0.045				
Fasting Blood Glucose	0.023	0.016	N/A				
Body Mass Index	N/A	0.031	0.011				
Smoking	N/A	0.036	0.005				

 \pm Individuals with diabetes only.

For all other outcomes, we also assume an ICC of 0.1 in our baseline power calculations and test sensitivity to revising the value downward to 0.05.

Cluster size

We aim to observe 10 individuals within each cluster at follow-up who have been exposed to an intervention (or are in the control group). To achieve this, we sample a larger number at baseline to allow for attrition and non-eligibility for the lottery intervention. This cluster size is set to achieve a balance between constraining the sample size while limiting costs incurred by surveying in many barangays.

Autocorrelation in outcomes

We will estimate treatment effects using ANCOVA. That is, the post-treatment outcome observed at follow-up will be regressed on an indicator of treatment group membership and the pre-treatment outcome, plus covariates observed at baseline. The coefficient on the treatment indicator is the estimated treatment effect. For given power and minimal detectable effect size, the required sample size is decreasing with the autocorrelation of the outcome (as well as the proportion of its variance that can be explained using baseline values of covariates).

Estimates of the autocorrelation in predicted 10-year CVD risk are not available, as far as we are aware. Age, sex, smoking and BMI, four of the five predictors of CVD risk used by Globorisk, are obviously very highly autocorrelated. The fifth predictor -a single visit measure of blood pressure -can be

expected to display much lower serial correlation. Blood pressure can vary depending on recent activity and diet, although we will follow a standard protocol for its measurement. It may also vary with the enumerator, although this will be minimized by use of an electronic meter and we can control for enumerator effects.

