In addition to the baseline value of the outcome, we will also control for a very larger battery of baseline covariates, including socioeconomic characteristics, medical history, health behavior and knowledge of risk factors.

Admittedly, we do not have a good idea of how the follow-up outcome will vary with all of these factors. We assume for the main power calculations a correlation of 0.6, which corresponds to an explained variance of 0.36. This would seem to err on the side of conservatism, given the very extensive set of covariates that can be used. We use the same value for all outcomes. We test sensitivity of the required sample size to reducing the autocorrelation to 0.4.

Attrition rate

We assume an attrition rate of 10%. This seems reasonably conservative given that the follow-up survey will be only 6-7 months after the baseline and we will make efforts to track respondents in the interim period. This will consist of obtaining the cellphone/ contact numbers of all respondents during the baseline interview. We shall instruct our survey contractor to develop and execute a plan to trace the respondents in between surveys. Their tracing strategy must include contacting each respondent at least once, and possibly twice, during the interim period to check if the respondents are still in the same location. Contact will be through a SMS, a telephone call and, if necessary, a personal visit. We will also engage a local field coordinator (other than the survey firm) to help out in validating the tracing reports of the survey firm, and in coordinating with Barangay Health Worker (BHW) or barangay captain about the whereabouts of respondents that we cannot locate.

Adjustment for refusal, ineligibility and item non-response

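### The draw rule (one winner per barangay, among claimants only) does not deliver the stated 1-in-10 chance or the expected value of 500 PHP used in H6c

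*Combined protocol and SAP*

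**What the plan says.** The chance is stated as fixed in two places. H6a in Section 3.2 says: "The lottery will have a selection probability of 10% and a prize of 5,000 PHP". Section 5.3 ties the same figure to the number of prizes: "There will be one prize per barangay giving each respondent a one in ten chances of winning P5000".

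H6c in Section 3.2 computes each person's risk premium R_i by subtracting the certainty equivalent from the "expected value of the lottery (EV = 500" PHP). It reads ψ1 in equation (6.3) as the response of risk-neutral people to an expected gain of that size.

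The mechanics are also in Section 5.3. Under the interview procedure, respondents are told that "their name will not be entered if they do not claim the ticket by attending the RHU/CHC for a checkup". Under the lottery draw, "Matching voucher and ticket numbers will be included in the list of lottery entries" and "One winner will be drawn from each barangay included in the lottery intervention", or none if nobody claims. The enumerator's script states the prize and the chance of winning, and the draft voucher gives the chance as 1 in X, with X still open.

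On numbers, Section 10.1 says: "We aim to observe 10 individuals within each cluster at follow-up who have been exposed to an intervention" (or are in the control group). It assumes 10% attrition, 14% ineligibility, 15% refusal, 5% item non-response and 60% compliance with the lottery offer (50% in sensitivity analysis).

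**The concern.** A fixed chance and a fixed number of winners cannot both hold when the number of entrants is random. The number of claimants is unknown when the voucher is handed over, and nothing in the plan caps or fixes entries at ten.

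Two things depend on the figure. First, the script announces a chance of winning, and the draw should honour whatever is announced. Second, H6c draws a money conclusion: if ψ1 is not significantly above zero, the perceived gains of a checkup are said to fall short of its costs by more than 500 PHP. That sentence needs an offer that respondents value as a 10% chance of 5,000 PHP.

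**Working it through.** **The stated expected value.** 0.10 × 5,000 = 500 PHP. It follows from the stated chance, so the question is whether the draw yields 10%.

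**What the baseline cluster size counts.** Table 6 is reproduced, to within one person of rounding, by baseline N = follow-up N / [(1 − 0.14) × (1 − 0.10 − 0.15 − 0.05)] = follow-up N / 0.602.
- Mean CVD risk: 2,899 / 0.602 = 4,815.6 (plan: 4,816).
- Binary outcomes: 3,021 / 0.602 = 5,018.3 (plan: 5,019).
- Per cluster: 10 / 0.602 = 16.61 (plan: 16.61).

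The 16.61 is thus counted before ineligible and refusing people drop out, and they receive no voucher.

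**Vouchers per barangay (n).** Vouchers go out at baseline, before attrition. The plan does not give n, but its loss rates bound it:
- 10 / 0.90 = 11.1
- 16.61 × 0.86 × 0.80 = 11.4
- 10 / (0.90 × 0.95) = 11.7
- 16.61 × 0.86 × 0.85 = 12.1

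**Chance for a claimant.** With n vouchers and independent claiming at rate p, the expected chance is [1 − (1 − p)^n] / (n p), close to 1 / (n p). Multiplying by 5,000 gives the expected value.

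| Claim rate p | Chance, n = 12.1 to 11.1 | Expected value (PHP) |
|---|---|---|
| 100% | 8.2-9.0% | 412-450 |
| 80% (assumed) | 10.3-11.3% | 515-562 |
| 70% (assumed) | 11.8-12.9% | 588-643 |
| 60% (main compliance figure) | 13.7-15.0% | 686-750 |
| 50% (sensitivity figure) | 16.5-18.0% | 823-900 |

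An average of ten claimants needs a claim rate of 10 / 12.1 to 10 / 11.1, about 82-90%.

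**Variation between barangays.** Take 12 vouchers and independent 60% claiming as an illustration. P(3 or fewer claim) = 0.015 and P(11 or 12 claim) = 0.020, so about 96.5% of barangays have 4 to 10 claimants, that is, a chance between 1/10 and 1/4. Exactly ten claim in 66 × 0.6^10 × 0.4^2 = 6.4%. No single X printed on the voucher would be true everywhere.

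**Other routes to 10%.**
- Averaging over claimants and non-claimants gives about 1/n = 8.2-9.0%. It gives 10% only with ten vouchers.
- 16.61 × 0.6 = 9.97 looks like ten claimants, but the 16.61 includes people who never get a voucher.

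**The case against.** **The 60% may not be a claim rate.** For mean CVD risk, the difference of 0.46 (11.35 − 10.89) with an SD of 2.27 (11.35 / 5) needs 383 per arm. Then 383 × (1 − 0.6²) × (1 + 9 × 0.1) / 10 = 46.6, rounded up to 47 clusters or 470 people, and 470 / 0.6² = 1,306, the figure in Table 6. Compliance therefore enters as the dilution of the effect, and it may be net of control-group attendance, which Section 10.1 expects but does not quantify. Control attendance of 10% or 20% would imply claiming of 70% or 80%. The plan also concedes that it has no firm evidence on take-up. This stands: 14-15% is one reading, not the plan's figure.

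**The analysis hardly depends on it.** Equations (6.1) and (6.2) use only the randomised offer. R_i is computed for everyone, offered the lottery or not, and can be read as a preference index for a reference gamble. The decision behind ψ1 is taken before the draw, on the odds announced. This also stands.

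**The direction is mostly benign.** On average, claimants get worse odds than stated only if more than about 82-90% claim. True, but the figure is still not the one delivered.

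**Stronger readings that the documents do not support.** A reader might infer that neighbours work out their true odds and so distort H6c. That is speculation: one winner per barangay appears as a study procedure, and nothing we could read says that respondents are told of it. A reader might also infer that the consent form misstates the odds. The form was not available to us, and the list of its contents in Section 12 does not mention odds.

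**Conclusion.** The inconsistency is real and minor. The stated 10% and 500 PHP are not what the stated draw rule delivers, and no section reconciles them. With 11 to 12 vouchers per barangay, the expected chance runs from about 8-9% (all claim), through about 10-13% (70-80% claiming), to about 14-15% and 690-750 PHP if 60% is the claim rate. These are averages under independent claiming; the actual chance differs by barangay.

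The lottery's role as an instrument is unaffected. In H6c, the 500 PHP reading of R_i and ψ1 is at risk only so far as respondents anticipate the real odds. If they act on an announced 1 in 10, it still describes the offer as they perceive it.

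**What to change.** Choose one of two, before vouchers are printed, and bring H6a, H6c and the voucher, script and draw text of Section 5.3 into line.

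1. **Make the draw match the statement.** Give each claimed ticket an independent 1-in-10 chance and print 1 in 10 on the voucher. The expected value is then 500 PHP in every barangay. Cost: the number of prizes becomes random. At 60% claiming it averages 0.10 × (6.7 to 7.3 claimants), about 0.7 per barangay against one now; if everyone claims it averages 1.1-1.2. Some barangays will have claimants but no winner: with seven claimants, 0.9^7 = 0.48, about half. That may matter for an offer whose credibility Section 5.3 takes care to protect.

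2. **Make the statement match the draw.** Keep one winner per barangay, tell respondents that the odds depend on how many people claim, and state in H6c that 500 PHP refers to a nominal 10% lottery, not the delivered one. Cost: wording only, but ψ1 can then no longer be read as the response to exactly 500 PHP.
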